In response to the paucity of data and the lackluster response to lifestyle interventions, two urgent research needs emerged: 1) to characterize the relationship of severe obesity with children's behavioral and environmental contexts and 2) to identify weight-gain trajectory data that differentiate children at high risk who need intensive intervention to promote healthy behaviors.¹⁵ The present project will provide important data for both the association of severe obesity with children's physical activity and sedentary

behavior (Objectives 1 and 3) and the identification of fat accumulation as a risk factor for inactivity (Objective 2).

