There is a dearth of data on the activity profiles of children and adolescents, particularly those with severe obesity and from ethnic minority groups. We will gather information on the location, frequency, intensity, and timing of physical activity and sedentary behavior in children during free-living conditions, providing precise profiles of children's activity patterns. To do so, we will use accelerometry, which is the gold standard to assess free-living physical activity and highly correlated with oxygen consumption or direct observation of physical activity.³²

This project makes three novel contributions to profiling children's activity: 1) by quantifying sedentary behavior with accelerometry, GPS, and EMA simultaneously, extensively characterizing free-living activity; 2) by examining differences in activity profiles by obesity status; and 3) by focusing on African American youth who are at particularly high risk for obesity and obesity-related health problems. Sedentary behavior, which is activity occurring at the lowest end of the intensity spectrum typically in the posture of sitting or lying down, has emerged as an independent risk factor for obesity-related comorbidities by our team₃₃ and others.³⁴ Identifying the contexts and facilitators of sedentary behavior will inform actionable strategies to reduce sedentary behavior in children's daily lives.

Obesity is an important risk factor for low physical activity and high sedentary behavior, but it is not clear how activity profiles differ based on obesity status. A study of 507 children aged 9 to 11 years demonstrated that accelerometer-measured MVPA was inversely associated with adiposity regardless of sedentary time or sleep duration,³⁵ yet associations were cross-sectional and adiposity was measured by bioelectrical impedance rather than DXA or MRI. The present project will build on prior work by examining the influence of longitudinal changes in fat, including depot-specific fat in the trunk and visceral regions, and subsequent health behaviors, with a focus on children with severe obesity.

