We will conduct a prospective epidemiological study to determine the effect of severe obesity on physical activity, sedentary behavior, and cardiometabolic risk factors among African American and White children and adolescents. Physical activity, sedentary behavior, cardiometabolic risk factors, and body composition will be assessed in each participant using gold standard, objective measures, with the first assessment (Year 0) in 2016-17 and the second assessment (Year 2) in 2018-19. We previously observed that children's physical activity and other health behaviors vary throughout the year based on school term versus school holiday.⁶⁰ Therefore, each child's Year 0 and Year 2 clinic visits will be scheduled at a consistent time of year to protect against changes due to the child being in school term or on a school holiday. Furthermore, we will use a scheduled enrollment to ensure that clinic visits are representative of both school term and school holidays.

Following an initial recruitment telephone screen or web-screen (followed by a telephone screen) to assess initial eligibility criteria, eligible participants will be scheduled for their Orientation visit at PBRC with their parent or legally authorized representative where participants will be formally oriented to the study by receiving detailed information on the purposes, goals, procedures, participant flow, and study timeline. Staff will obtain signed informed consent and child assent before participants take part in any of the study-related procedures. Participants will be given the GPS and accelerometer devices as well as instructions on how to wear them for the next week. Participants will also be given the EMA application on their personal cell phones or a provided mobile device along with instructions on how to respond to the prompts for the next week. Participants will be introduced to the ASA-24 dietary intake tool and provided instructions on how to complete two separate recalls from their home computer prior to the Year 0 clinic visit. Participants and parents may be asked to complete surveys on the devices while waiting. At the conclusion of the Orientation. Parents may receive reminders from staff for all tasks required of participants between orientation and Year 0.

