Participants will be fasting at the Year 0 visit. Measurements including anthropometry, blood draw, urine pregnancy test, body composition, dietary intake, activity monitor tracking equipment collection, and all remaining surveys will take place during the clinic visits. Participants must be accompanied by a parent or legally authorized representative at the clinic visits.

Approximately 10 days prior to the Year 2 visit, participants will pick up an accelerometer and GPS device to wear for 7 days and return at the Year 2 clinic visit. Participants will also be given instructions on how to complete two trials of the ASA-24 dietary intake tool from their home computer prior to the Year 2 clinic visit. Participants will return to clinic approximately 2 years (+/- 6 months) after their Year 0 visit for a Year 2 visit, in which all procedures collected during Year 0 will be repeated. **Table 2** includes a list of all measurements occurring at both visits. Parents may receive reminders from staff for all tasks required of participants between orientation and Year 2.

Measurements

	Orientation	Year 0	Year 2
Informed consent/assent	Х		
Anthropometry (Height, weight, waist size)		Х	Х
Blood Pressure		Х	Х
Body Composition (DXA, MRI)		Х	Х
Blood Draw		Х	Х
Urine Pregnancy Test (eligible females only)		Х	Х
Dietary Intake (ASA-24)		Х	Х
Family environment surveys		Х	Х
Neighborhood environment surveys		Х	Х
Body image and mood surveys		Х	Х
Global Positioning System (GPS)	7-days		7-days
Physical Activity (Actigraph GT3X+)	7-days		7-days
Ecological momentary assessment (eMA)	7-days		

Table 2. Study procedures

Description of tests and procedures

Anthropometry

Weight- Anthropometry will be measured to the nearest 0.1 cm (0.1 kg for weight). All measures are taken twice with the analyzed value being the average of both measurements. If the measures differ by greater than 0.5 units, a third measurement will be taken to replace the discrepant value. Participants wear only a hospital gown and undergarments while being weighed.

Height- Standing height will be measured using a Harpenden stadiometer (Holtain Limited, Crymych, UK). Participants will remove shoes, stand upright with heels and back against the stadiometer, inhale, and hold breath while an assessor provides traction to align the participant's head along the Frankfort Horizontal Plane during measurement. Weight will be measured using a Michelli GSE 460 scale (G.T. Michelli Co., Baton Rouge, LA).

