Analyses to test Hypothesis 2 will be conducted using a series of linear regression models (i.e. linear mixed effects models). Based on difference score between Years 0 and 2 for total body fat, the group will be divided into two dichotomous groups using percentiles: high fat gainer (HFG) and low fat gainer (LFG). These variables will be used to predict changes in physical activity, sedentary behavior, and each cardiometabolic risk factor in linear mixed effect models. Covariates will include age, sex, dietary intake, and race. School term vs. school holiday will be considered as an additional covariate if time of year is significantly associated with the independent and dependent variables. Secondary analysis will use MRI and DXA as covariates in the model (namely the visceral, trunk, and total body fat). As previously reported, variable select criteria (including LASSO and support vector machine) will be used to determine which combination of these variables best explains the variance in the data. The full model will enable the comparison the accumulation of imaging-based body composition measures vs. BMIz alone and their associations with change in physical activity, sedentary behavior, and cardiometabolic risk factors in children. Finally, there are no standard accepted definitions of pediatric severe obesity to dichotomize participants based on MRI or DXA measures of body fat. Therefore, receiver operating characteristic curves will be created to estimate the value at which visceral, trunk, and body fat best correspond with the BMI definition of severe obesity (i.e. $BMI \ge 120\%$ of the 95th percentile1). Clinically relevant cut-points of severe obesity based on total, trunk, and visceral body fat will be established among this diverse cohort of adolescents.

Power analysis

Objective 1:

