Objective 2:

The primary outcome for the second objective is the relationship between total fat accumulation and change in sedentary behavior. Based on data from Berkey et al.,75 we estimate an overall change in sedentary behavior of 12 minutes/day increase in the HFG and 3.6 minutes/day increase in the LFG over a two-year period. **Table 6** shows sample sizes required to detect various differences for the change between groups. With a sample size of up to 345, this will provide at least 80% power for detecting a difference in the change between groups of 8.4 minutes/day, allowing for the anticipated 25% dropout. Therefore, with our sample size of up to 345 participants, we will have sufficient power to detect a difference between the HFG and LFG groups.

Change in minutes	Change in minutes	Change between	Standard deviation	Minimum sample	Total sample size
of sedentary time	of sedentary time	groups	of change between	size	(allows for 25%
for HFG	for LFG		groups		dropout)
12	2.4	9.6	24	194	259
12	3	9.0	24	220	293
12	3.6	8.4	24	255	Up to 345
12	4.2	7.8	24	292	389

Table 6. Difference in changes in sedentary time between the high fat vs. low fat gainer group. *Note.* HFG is the group classified as high fat gainers; LFG is the group classified as low fat gainers.

Secondary analyses based on the second objective will include modeling the relationship between fat mass accumulation and change in physical activity. Using data from Berkey et al.,75 we estimate an overall decrease of 19.2 minutes/day of MVPA in the HFG and a decrease of 4.8 minutes/day of MVPA in the LFG over a two-year period. With a sample size of up to 345 (including anticipated dropout), this will provide 93.4% power for detecting a difference in the change between groups of 14.4 minutes/day.

Contingencies

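### Objective 2 relates fat change to behavior change over the same two years: it can show a concurrent association, but not that fat accumulation is a risk factor for inactivity

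*Combined protocol and SAP*

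**What the plan says.** **The analysis.** Under Statistical Analysis, Objective 2, the exposure is formed "Based on difference score between Years 0 and 2 for total body fat" and split by percentiles into high fat gainers (HFG) and low fat gainers (LFG). Then: "These variables will be used to predict changes in physical activity, sedentary behavior, and each cardiometabolic risk factor in linear mixed effect models". The adjustment set is short: "Covariates will include age, sex, dietary intake, and race", with school term or holiday added if it is associated with exposure and outcome. Under Power analysis, Objective 2: "The primary outcome for the second objective is the relationship between total fat accumulation and change in sedentary behavior".

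**The timing.** Study Design gives two waves, "with the first assessment (Year 0) in 2016-17 and the second assessment (Year 2) in 2018-19". Body composition is measured at the clinic visits (Table 2). At the second wave, "Approximately 10 days prior to the Year 2 visit, participants will pick up an accelerometer and GPS device to wear for 7 days", returning the devices at that visit. At the first wave the devices are handed out at Orientation and worn in the following week, before the Year 0 visit.

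**The claims.** Hypothesis 2 in Study Objectives says fat accumulation will be associated with changes in behavior. Other text goes further:
- Objective 2 itself speaks of what fat accumulation contributes to behavior change.
- The Background section on severe obesity and fat accumulation promises "the identification of fat accumulation as a risk factor for inactivity (Objective 2").
- The Background section on activity profiles describes "examining the influence of longitudinal changes in fat, including depot-specific fat in the trunk and visceral regions, and subsequent health behaviors".

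**The concern.** A risk factor should precede what it is said to predict. Here exposure and outcome are both differences between the same two waves, so no behavior is measured after the fat-gain interval. If anything the order is slightly the other way, since each accelerometer week precedes the visit at which fat is scanned.

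The competing explanation comes from the protocol. The Description of Problem to be Solved treats inactivity as an established contributor to obesity, and the section on the 24-hour dietary recall refers to effects of activity and sedentary behavior on obesity. A positive Objective 2 result is what that direction would produce. The project exists to find intervention targets, and the target differs if fat gain follows sedentary time rather than leading to it. More participants or better measurement would not resolve this.

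**Working it through.** **Inputs.** From Power analysis, Objective 2 and Table 6: expected change of +12 min/day in HFG and +3.6 in LFG, difference 12 − 3.6 = 8.4; SD of change 24; minimum sample 255; total up to 345; 80% power; 25% dropout. Alpha of 0.05 is stated for Objective 1; I assume it applies here, two-sided. The plan says only that percentiles define the groups; I assume a median split.

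**Step 1: reproduce the plan's figure.** n per group = 2 × (1.960 + 0.842)² × 24² / 8.4² = 128.2, rounded up to 129, so 258 in total against the stated 255. Allowing for dropout, 258 / 0.75 = 344 against up to 345. Power with 345 × 0.75 ≈ 258.8 evaluable is 80.4% (80.1% with the t distribution). The sample size is not at issue.

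**Step 2: convert the planned difference to a correlation.** For jointly normal changes and a median split, the group difference is 2 × √(2/π) × r × SD = 1.596 × r × 24. Setting this to 8.4 gives r = 8.4 / (1.596 × 24) = 8.4 / 38.3 = 0.22. A correlation has no direction.

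**Step 3: simulate three causal structures at that correlation.** 258 participants, median split on fat change, two-sample t test on sedentary change, 4,000 replicates each, no covariates.

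| What generates the correlation | Mean HFG − LFG (min/day) | Tests positive |
|---|---|---|
| Fat change drives sedentary change | 8.4 | 81% |
| Sedentary change drives fat change | 8.4 | 81% |
| Shared cause only | 8.4 | 81% |

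The rate is slightly above 80% because 24 is taken as the overall SD, so the within-group SD is √(24² − 4.2²) = 23.6.

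**Step 4: look for time order elsewhere in the plan.**
- Objective 2: the listed covariates include neither Year 0 behavior nor Year 0 fat, and there is no lagged term. The secondary analyses add imaging measures and variable selection, which do not supply time order.
- Objective 1: severe obesity at Year 0 is related to later change, so there is some time order, but for obesity status rather than fat accumulation.
- Reverse direction: no model relates Year 0 behavior to later fat change.

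**The case against.** The strongest reply is that the tested claim is already associational. Hypothesis 2 is worded that way, the Objective 2 analysis text speaks of associations, and the power section defines the outcome as a relationship. That stands. A reader might infer that Objective 2 cannot test its own hypothesis; the documents do not support that. The mismatch is between the analysis and the directional wording in the objective and the Background, one sentence of which describes the project as a whole.

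A reader might also infer that the plan contains no time-ordered analysis at all. Objective 1 rules that out. Its secondary analysis even adds visceral, trunk and total fat, though without stating the imaging time point or adjusting for Year 0 behavior. The gap is specific to Objective 2 and to the untested reverse direction.

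The simulation is open to the charge of circularity, and fairly so: r = 0.22 is solved from the plan's own effect size, so each structure must return roughly the plan's own power. It shows that the test cannot discriminate, not that a reverse effect of that size exists. The documents give no size for one.

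Finally, lagged models from two waves do not settle direction. Year 0 fat is a level, not accumulation, and stable confounding and measurement error remain. This also stands and limits what the added models may be used for.

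**Conclusion.** The point holds as a limit on inference. The change-on-change model is suitable for Hypothesis 2. It does not support calling fat accumulation a risk factor for inactivity, claiming effects on later behavior, or attributing behavior change to fat accumulation. A significant result is as likely under the reverse direction or a shared cause as under the intended one when each produces the same correlation.

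The 0.22 and 81% figures are illustrative and rest on a median split, normal changes and no covariates. The main conclusion does not depend on them: it follows from exposure and outcome sharing one interval. No sample size or planned test changes. Behavior after the fat-gain interval would need a later measurement, which is not planned.

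**What to change.** 1. Keep the HFG/LFG change-on-change model and state in advance that its result will be reported as concurrent association.
2. Align the wording of Objective 2 and the two Background statements with Hypothesis 2.
3. Add two prespecified secondary models using the existing covariates:
   - Year 2 sedentary time on Year 0 total body fat, adjusted for Year 0 sedentary time.
   - Year 2 total body fat on Year 0 sedentary time, adjusted for Year 0 total body fat.
4. Report both, whatever they show, as evidence on temporal order only. State that Year 0 fat is a level rather than accumulation and that confounding and measurement error remain. Do not use them to license a causal or directional claim about fat accumulation.

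Fat gain from the earlier WAIST assessment to Year 0 would precede the outcome. However, Recruitment Methods gives only about 193 re-contactable, age-eligible children, before refusals and dropout, against the 255 in Table 6. It should be omitted or labeled exploratory.

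The cost is a wording change, two extra models on measurements already scheduled, and a more modest conclusion for Objective 2.

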The primary outcome for the first objective is change in minutes of sedentary behavior between Year 0 and Year 2 (i.e. Year 2 values minus Year 0 values). Baseline estimates for the two groups were calculated using the WAIST cohort data (from the 2010-11 assessment). Based on data from Berkey et al.,75 the SO group is assumed to increase their sedentary time by 30 minutes/day at year 2, while smaller increases in sedentary time is expected for the NSO group (**Table 5**). A minimum of 334 participants is needed to ensure a well-powered study with significance level of $\alpha = 0.05$, 80% power to detect a 24 minute difference change in sedentary behavior between the two groups, and allowing for a dropout rate of 25%. Therefore, our sample size of up to 345 participants will be sufficient.

Change in minutes/day of sedentary time for NSO group	Change in minutes/day of sedentary time for SO group	Difference in change between groups	Standard deviation of change between groups	Minimum sample size	Total sample size (allows for 25% dropout)
2.4	30.0	27.6	69.6	202	253
3.6	30.0	26.4	69.6	222	278
4.8	30.0	25.2	69.6	242	303
6.0	30.0	24.0	69.6	266	334

Table 5. Difference in changes in sedentary time based on severe obesity status. *Note.* NSO is the group classified as not severely obese; SO is the group classified as severely obese.

Note. NSO is the group classified as not severely obese; SO is the group classified as severely obese.

Secondary analyses will include change in daily MVPA minutes between years and change in days/week of physical activity (\geq 60 minutes MVPA/day) between years. Power analysis was conducted on these outcomes, using the WAIST cohort and data from Nigg et al.,76 and our sample size will have power of 93.8% and 90.4% to detect a significant difference in change in daily MVPA minutes and change in days/week of physical activity, respectively.

Contingencies

Based on national reference data, it is possible that very few or no severely obese children meet the healthy behavior or cardiometabolic health criteria (e.g. no severely obese child attains ≥ 60 minutes of MVPA/day; no severely obese child has a waist circumference < 90th percentile). If this is the case, the dichotomous dependent variable will be adjusted to be quartiles, so that the analyses is interpreted as the likelihood of a severely obese child being in the top (healthiest) quartile of the health behavior or cardiometabolic health criteria for the overall cohort.

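### The Objective 2 change models leave out the Year 0 value of the outcome, forgoing precision and leaving the fat-gainer contrast dependent on any starting difference between the groups

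*Combined protocol and SAP*

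**What the plan says.** The Statistical Analysis section, Objective 2, forms the exposure from the Year 0 to Year 2 difference in total body fat: "the group will be divided into two dichotomous groups using percentiles: high fat gainer (HFG) and low fat gainer (LFG"). The percentile is not given. The model follows: "These variables will be used to predict changes in physical activity, sedentary behavior, and each cardiometabolic risk factor in linear mixed effect models". Then: "Covariates will include age, sex, dietary intake, and race". School term versus holiday may be added conditionally, and secondary models bring in the MRI and DXA fat measures. Neither this section nor any other adds the Year 0 value of the outcome.

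The Power analysis, Objective 2, names the primary outcome: "The primary outcome for the second objective is the relationship between total fat accumulation and change in sedentary behavior". Change is defined under Objective 1 as "change in minutes of sedentary behavior between Year 0 and Year 2 (i.e. Year 2 values minus Year 0 values"). The Table 6 row that sets the sample size reads "12 3.6 8.4 24 255 Up to 345", and the text says "this will provide at least 80% power for detecting a difference in the change between groups of 8.4 minutes/day".

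Under Study Design, sedentary behavior is to be assessed in each participant at both time points. Table 2 places the first accelerometer week at Orientation, before the Year 0 clinic visit. The Contingencies text under Objective 3 expects some missing accelerometer data and plans multiple imputation.

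**The concern.** A change score is usually negatively correlated with its starting value, because children who start high tend to rise less. The Year 0 value is therefore likely to be a useful predictor of the change, and leaving it out gives up precision.

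The second consequence is comparability. High and low fat gainers are formed by what happened to them, not by randomisation, so they may differ in sedentary time at Year 0. The protocol's Description of Problem treats inactivity as an established contributor to obesity, so such a difference is plausible. If it exists, part of the difference in change reflects where the groups started. An association could then be partly hidden or partly created. The same applies to MVPA and to each cardiometabolic factor in its own change model.

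In Objective 2 the fat gain is measured from Year 0 onward, so the Year 0 outcome comes before the exposure as defined. In Objective 1 severe obesity is already present at Year 0, so baseline adjustment would change the question asked there.

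**Working it through.** **Inputs.** From Table 6: difference 8.4 min/day (12 − 3.6), SD of change 24, minimum sample 255, total up to 345. Dropout is 25%. Alpha 0.05 is stated for Objective 1 only; two-sided testing and equal groups are assumed because they reproduce Table 6 closely. The Year 0 to Year 2 correlation (rho) is not in the documents and is varied.

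**Plan's figure.** Total n = 4 × (1.960 + 0.842)² × 24² / 8.4² = 256.3, or 129 per group after rounding up, 258 in all, against 255 stated. Enrolment: 258 / 0.75 = 344, against 345. With 258 completers (345 × 0.75 = 258.75), noncentral-t power is 80.0%. The plan's figure holds, and it is computed from the SD of the unadjusted change.

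**Precision.** Let S be the between-child SD at one visit, equal at both visits. The variance of change is 2S²(1 − rho). After adjusting for Year 0 the residual variance is S²(1 − rho²). The ratio is (1 + rho)/2, so the adjusted SD is 24 × √((1 + rho)/2). Holding the SD of change at 24 also fixes S = 24 / √(2(1 − rho)).

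| rho | implied S (min/day) | adjusted SD | power | gain (points) |
|---|---|---|---|---|
| 0.3 | 20.3 | 19.35 | 93.5% | 13.5 |
| 0.5 | 24.0 | 20.78 | 89.9% | 9.9 |
| 0.7 | 31.0 | 22.13 | 85.9% | 5.9 |
| 0.8 | 37.9 | 22.77 | 83.9% | 3.9 |
| 0.9 | 53.7 | 23.39 | 81.9% | 1.9 |

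These figures assume little correlation between group and baseline. At rho = 0.5 and n = 255, a group–baseline correlation of 0.3 lowers adjusted power from 89.7% to 86.8%. With a 25/75 split instead of a median split (also n = 255), power is 67.7% unadjusted and 79.8% adjusted at rho = 0.5.

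**Baseline difference.** Let D be the Year 0 mean of high gainers minus that of low gainers. The adjusted contrast equals the change contrast plus (1 − rho) × D. For a median split of a normally distributed fat gain whose correlation with Year 0 sedentary time is r, D = r × S × 2√(2/π) = 1.596 × r × S.

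| rho | r | D (min/day) | (1 − rho) × D |
|---|---|---|---|
| 0.5 | 0.1 | 3.83 | 1.9 |
| 0.5 | 0.2 | 7.66 | 3.8 |
| 0.9 | 0.1 | 8.56 | 0.9 |
| 0.9 | 0.2 | 17.13 | 1.7 |

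The two contrasts therefore differ by about 1 to 4 min/day against a target of 8.4. The values of r are assumptions. A positive D makes the unadjusted contrast the smaller one; a negative D makes it the larger.

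**The case against.** **No planned power is lost.** A reader might infer that the study falls about 10 points short of its stated power. It does not: the 80% was calculated for the unadjusted change, which is the analysis described. The 10-point figure is a forgone gain at rho = 0.5 only, and that value with an SD of change of 24 forces a between-child SD of just 24 min/day. The protocol puts adolescent sitting at 7.5 hours (450 minutes) a day, so this is a spread of about 5% (24/450). A larger spread implies a higher rho and a gain toward the low end. This objection stands.

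**The unadjusted contrast is not shown to be biased.** A reader might also infer that it is wrong and the adjusted one right. The documents do not support that. In the power section 8.4 is itself the raw difference in change, so simulations that treat 8.4 as the adjusted effect do not describe the plan's own target. With non-randomised groups the two models answer different questions and can disagree (Lord's paradox). Fat gain before Year 0 may already have shaped Year 0 sedentary time.

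**Measurement error can make adjustment overshoot.** In simulations with rho = 0.5, r of 0.1 and 0.2, and 8.4 taken as the true adjusted effect, reliability of 0.8 gives adjusted averages of 8.8 and 9.2 and unadjusted averages of 7.1 and 5.8. At reliability 0.5 the unadjusted estimate averages 8.4 and the adjusted 9.7 and 11.1. As few as 4 valid accelerometer days are accepted, so some error is certain. This rules out replacing one analysis with the other, but it supports showing both.

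**Mixed models might already include baseline.** They would if Year 0 and Year 2 values were both modelled as outcomes. The text, however, makes the change the response.

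**Missing data.** Year 0 accelerometry is planned for each participant, not guaranteed. A child without it has no observed change score either, so adjustment costs no further participants.

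**Conclusion.** The concern holds as an omission with a modest, assumption-dependent cost. The Year 0 outcome is planned for each participant, precedes the fat gain that defines the groups, and is absent from the Objective 2 covariates. The stated 80% power is correct for the planned analysis. Adjustment would add roughly 2 to 14 points for rho from 0.9 to 0.3, assuming an SD of change of 24, 258 completers, equal groups and equal variances at both visits. A larger between-child SD points to the low end.

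The more important reason to act is that the unadjusted contrast carries (1 − rho) × D. Under r of 0.1 to 0.2 and rho of 0.5 to 0.9 this is about 1 to 4 min/day, enough to matter against 8.4. Its actual direction and size cannot be known from the documents, and neither estimator is always the unbiased one.

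A separate point affects Objective 2 power more. The SD of change for the same outcome is 69.6 in Table 5 and 24 in Table 6. If 69.6 applied here, power for 8.4 min/day would be about 16% unadjusted and 20% adjusted at rho = 0.5. Those two figures need reconciling in their own right.

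**What to change.** In the Statistical Analysis section, Objective 2, prespecify for each change model a version that adds the Year 0 value of that outcome as a continuous covariate: Year 0 sedentary min/day, Year 0 MVPA, or the Year 0 level of the risk factor. Report it beside the planned unadjusted change contrast, and state that a fat-gain association will be interpreted with caution if the two disagree. Leave the Objective 1 main contrast unchanged.

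The cost is a sentence or two of text and one degree of freedom per model, with no new data. The downside is possible overshoot of the adjusted estimate when the Year 0 value is measured with error; reporting both estimates makes that visible.
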